## **8.1.4 Other Assessments**

### **8.1.4.1 Quality of Life Questionnaire**

The EQ-5D-3L is a standardized measure of health status that provides a simple, generic measure of health for clinical and economic appraisal. The questionnaire, which is designed for self-completion by respondents, is applicable to a wide range of health conditions and treatments [[EuroQol Group, 1990](#)]. The questionnaire is to be completed at Visits 1 and 8.

The EQ-5D-3L consists of 2 parts:

- A descriptive profile, comprising the following 5 dimensions: mobility, self-care, usual activities, pain / discomfort, and anxiety / depression. Subjects rate each dimension based on 3 levels of severity (ie, no problems, some problems, extreme problems).
- A vertical, visual analog scale (VAS), on which the subject rates their overall health from 'Best imaginable health state' to 'Worst imaginable health state'.

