Following hospitalizations related to coronary, cerebral, or peripheral ischemia, counts of occurrences of discharge by category (to home with additional care, home without additional care, rehab, and skilled nursing facilities) will be summarized.

The EQ-5D-3L is a patient self-assessment of 5 dimensions of health-related quality of life: mobility, self-care, usual activities, pain or discomfort and anxiety or depression. Each dimension is measured on a 3-point scale where a higher score corresponds to a worse health state. Scores from the individual dimensions will be utilized to calculate an overall utility score for each patient using the algorithm specified by the developers of the instrument [EuroQol Group, 1990]. The EQ VAS is a continuous 100-point integer scale from 0 (the worst health you can imagine) to 100 (the best health you can imagine).

Response to each of the 5 dimensions will be descriptively summarized. For each treatment, shift tables will be employed indicating the number of subjects whose response falls into a grid defined by the baseline value on 1 axis and the post-treatment value on the other axis. To compare treatments on each dimension, the number (%) of subjects with improvement, no change, or worsening from baseline to the post-treatment value will be analyzed using a chi-square test for a 2 x 3 contingency table with ordered categories of response.

Both the utility score and the EQ VAS are continuous response variables describing the patient's self-assessment of their health status at baseline and post-treatment. Descriptive statistics including the mean, median, SD, minimum and maximum will be provided at baseline, post-treatment and for the change from baseline. The change from baseline will be compared between treatments employing an analysis of variance model including terms for treatment, index MI type, index MI management, region, an interaction term for index MI type by index MI management, age (as a continuous variable), diabetes, peripheral artery disease, and history of prior MI (excluding index MI).

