4.6.2 Interim Sample Size Re-estimation

MACE rates will be monitored by CSLB and the Executive Committee, using blinded data, to reach a decision on the final sample size prior to completion of the enrollment phase. The observed blinded event rate will be based on a 90-day Kaplan-Meier estimate using a time-to-event approach with appropriate censoring to account for unobserved data. If the observed blinded event rate is higher than expected, then fewer subjects than 17,400 may be enrolled, with a minimum of approximately 15,000 subjects, corresponding to a placebo 90-day event rate of 7.4%. Conversely, if the observed, blinded event rate is less than expected, more subjects may be enrolled, but the increase would be capped at approximately 20,600 subjects, corresponding to a placebo 90-day event rate of 5.4%. The decision regarding sample size adjustment will be made when approximately 75% of subjects have been enrolled or approximately 75% of events have been accrued, whichever occurs first, with communication to sites occurring approximately 3 months prior to close of enrollment. The actual number of subjects to be enrolled, within the pre-specified range (15000 to 20600), will be determined by the Executive Committee and sponsor and chosen to provide a total of approximately 1004 events for the primary outcome. A subgroup analysis will be performed at the time of

final reporting to assess the consistency of primary MACE results for cohorts enrolled before and after the site communication on sample size re-estimation.

The table below illustrates the sample size associated with hypothetical placebo 90-day event rates assuming a 20% risk reduction attributable to CSL112. Since the sample size re-estimation will be performed using blinded data, the observed event rate will be compared to the pooled event rate shown in Table 4-3 below.

Table 4-3 Event Rate for Re-estimating Sample Size

Event Rate (%)			Sample Size
Placebo	CSL112	Pooled	
7.40	5.92	6.66	15,000
6.40	5.12	5.76	17,400
5.40	4.32	4.86	20,600

5 Changes in the Conduct of Protocol Planned Analyses

Not applicable

6 Study Analysis Sets

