8.2.6 Change from Baseline

Change from baseline will only be calculated for measures that have post-baseline records.

Change from baseline is calculated as:

$$(\text{Visit value}) - \text{Baseline value}.$$

Percentage change from baseline is calculated as:

$$((\text{change from baseline}) / \text{baseline value}) * 100$$

If either the baseline or visit value is missing, the change from baseline and percentage change from baseline is set to missing as well.

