The relationship between medical resource utilization and treatment with CSL112 will be descriptively summarized. The endpoints of medical resource utilization including the number of hospitalizations, length of hospital stay (days), CCU or ICU stay (days) and number of select surgeries/select procedures related to hospitalization for coronary, cerebral, or peripheral ischemia will be treated as count data for the purpose of analysis. For each subject, total counts either in number of admissions or duration of stay will be derived across all hospitalizations occurring during the 90 day period from randomization. The analyses of these endpoints will use a negative binomial regression model as described for the key secondary endpoint of CV hospitalizations described in [Section 10.2.1](#). Discharge to following CV hospitalization will be descriptively summarized with counts and percentages in each category by treatment arm.

The EQ-5D-3L is a patient self-assessment of five dimensions of health-related quality of life: mobility, self-care, usual activities, pain or discomfort and anxiety or depression. Each dimension is measured on a 3-point scale where a higher score corresponds to a worse health state. Scores from the individual dimensions will be used to calculate an overall utility score for each patient using the algorithm specified by the developers of the instrument [[EuroQoL, 2015](#)]. The EQ VAS is a continuous 100 point integer scale from 0 (the worst health you can imagine) to 100 (the best health you can imagine). Further details can be found in [Appendix 15.2](#).

Response to each of the five dimensions will be descriptively summarized. For each dimension and treatment, shift tables will be employed indicating the number of subjects whose response falls into a grid defined by the baseline value on one axis and the post-treatment value on the other axis. To compare treatments on each dimension, the number (%) of subjects with improvement, no change, or worsening from baseline to the post-treatment value will be analyzed using a chi-square test for a 2 x 3 contingency table with ordered categories of response.

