Both the utility score and the EQ VAS are continuous response variables describing the patient's self-assessment of their health status at baseline and post-treatment. Descriptive statistics including the mean, median, SD, minimum and maximum will be provided at baseline, post-treatment and for the change from baseline. The change from baseline will be compared between treatments employing an analysis of variance model (ANOVA) including terms for treatment, region, type of index MI (STEMI vs NSTEMI), management of index MI (PCI vs. medical management), age (as a continuous variable), diabetes, peripheral artery disease, prior history of MI, and a term for interaction between index MI type and index MI management.

Additional Exploratory Efficacy Endpoints

The following additional exploratory efficacy endpoints will be analyzed based on the ITT population. Endpoints consisting of other time points (90, 180, or 365 days) not explicitly listed in this document will also be analyzed.

1. Time-to-occurrence of all-cause death from the time of randomization through 90, 180 days and end of study

2. Time to occurrence of non-COVID-19 related death from the time of randomization through day 365. All deaths resulting from COVID-19 will be censored in this analysis
3. Time-to-first occurrence of CV death or MI from the time of randomization through 90 days
4. Time to first occurrence of CV death, MI, or stroke from the time of randomization through the end of study
5. Time-to-first occurrence of all-cause death, MI, or stroke from the time of randomization through 90 days
6. Time to occurrence of CV death from the time of randomization through 180 days and end of study
7. Time-to-first occurrence of MI from the time of randomization through 180, 365 days and end of study
8. Time-to-first occurrence of stroke from the time of randomization through 180, 365 days and end of study
9. Time to occurrence of thrombotic (ischemic) strokes with hemorrhagic conversion from the time of randomization through day 365
10. Time to occurrence of hemorrhagic stroke from the time of randomization through day 365
11. Time-to-first occurrence of stroke including sub-arachnoid stroke from the time of randomization through days 90, 180 and 365
12. Medical resource utilization from the time of randomization through 180 and 365 days:
 - a. Number of total hospitalizations
 - b. Length of hospital stay
 - c. Number of cardiac care unit (CCU) or intensive care unit (ICU) days

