15.2 Analysis of Questionnaire EQ-5D-3L

The EQ-5D-3L is a patient self-assessment of five dimensions of health-related quality of life (HRQOL): mobility, self-care, usual activities, pain or discomfort and anxiety or depression. Each dimension is measured on a 3-point scale (no problem, some problems, and extreme problems) where a higher score corresponds to a worse health state. The score on each dimension is analyzed separately. In addition, patient's self-assessment on all five dimensions assigns each patient to one of 243 possible health states (ie, from 11111 to 33333 where each digit corresponds to one of the five dimensions and each number corresponds to the rating on each dimension). Each of these 243 possible health states is then mapped to a specific utility score which will be analyzed as a continuous score as well as be employed in a cost-effectiveness analysis. The tariff to be used for the mapping is given by [\[Dolan and Roberts, 2002\]](#). The UK-specific scoring algorithm will be utilized in the analysis and is illustrated with the following example: a subject provides the following responses: Mobility=No problems, Self-care=No problems, Usual Activities=Moderate problems, Pain/Discomfort=Moderate problems, Anxiety/Depression=Extreme problems. Therefore, the response sequence is 11223.

The utility score for the subject with example sequence 11223 = 0.255 is calculated as shown in [Table 15-1](#).

Table 15-1 EQ-5D-3L Scoring Algorithm

Domain Score	Tariff	Example Subject with Sequence 11223 Utility Score = -0.255	
Full health (11111)	1.000		1.000
Constant term (for any dysfunctional state):	-0.081		-0.081
Mobility level 1:	0	✓	0
Mobility level 2:	-0.069		
Mobility level 3:	-0.314		
Self-care level 1:	0	✓	0
Self-care level 2:	-0.104		
Self-care level 3:	-0.214		
Usual activities 1:	0		
Usual activities 2:	-0.036	✓	-0.036
Usual activities 3:	-0.094		
Pain/discomfort 1:	0		
Pain/discomfort 2:	-0.123	✓	-0.123
Pain/discomfort 3:	-0.386		
Anxiety/depression 1:	0		
Anxiety/depression 2:	-0.071		
Anxiety depression 3:	-0.236	✓	-0.236
At least one domain at 3 (N3):	-0.269		-0.269

Any missing values which are coded as '9' will be set to missing (and hence no health state value will be calculated). Ambiguous values (eg, 2 boxes ticked for a single dimension) will be treated as missing values. If 1 or more domains are missing the HSV will not be calculated

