The EQ VAS (visual analogue scale) is a continuous 100 point integer scale from 0 (the worst health you can imagine) to 100 (the best health you can imagine). Missing values will be recorded as '999' but will be replaced by a missing value for all analyses. Ambiguous values (e.g., the line crosses the VAS twice) will be treated as missing values.

Analysis of the five dimension scores:

Each of the five dimension scores will be descriptively summarized and analyzed separately. For each treatment, shift tables will be employed indicating the number of patients whose score falls into a grid defined by the baseline value on one axis and the post-treatment value on the other axis. To compare treatments on each dimension, the number of patients with improvement, no change and worsening from baseline to the post-treatment value will be

analyzed using a chi-square test for a 2 x 3 contingency table with ordered categories of response.

Analysis of the EQ VAS and Utility Score:

Both the EQ VAS and the utility score are continuous response variables describing the patient's self-assessment of their health status at baseline and post-treatment. Descriptive statistics including the mean, median, SD, minimum and maximum will be provided at baseline, post-treatment and for the change from baseline. The difference between baseline and post-treatment will be compared between treatments employing an analysis of variance model (ANOVA) including terms for treatment, each of the stratification factors (region, type of MI (STEMI vs NSTEMI) and management of MI (PCI vs. medical management)).

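### The SAP gives two different models for change in EQ-5D-3L utility and EQ VAS, and neither they nor the protocol model adjusts for the baseline score

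*SAP*

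**What the plan says.** Three passages specify the treatment comparison for change in utility score and EQ VAS.

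- **Protocol 10.3.2.4.1:** an analysis of variance on change. Arm and the three randomization strata come first. It then names "an interaction term for index MI type by index MI management, age (as a continuous variable), diabetes, peripheral artery disease". Earlier infarction closes the list.
- **SAP 10.4:** an ANOVA on change from baseline, again with arm and the three strata. The remainder reads "age (as a continuous variable), diabetes, peripheral artery disease, prior history of MI, and a term for interaction between index MI type", crossed with PCI or medical treatment.
- **SAP Appendix 15.2:** an ANOVA on the baseline to post-treatment difference. Here the complete list is "including terms for treatment, each of the stratification factors (region, type of MI (STEMI vs NSTEMI) and management of MI (PCI vs. medical management". Nothing follows it.

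SAP 10.4 points to the appendix at the end of its scoring paragraph: "Further details can be found in" Appendix 15.2. The appendix is headed "15.2 Analysis of Questionnaire EQ-5D-3L" and contains analysis paragraphs as well as the scoring algorithm. SAP Section 5, on changes from the protocol analyses, reads "Not applicable".

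On data collection, Protocol 8.1.4.1 says: "The questionnaire is to be completed at Visits 1 and 8". SAP 8.2.6 says: "If either the baseline or visit value is missing, the change from baseline and percentage change from baseline is set to missing as well".

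**The concern.** There are two separate points.

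First, one endpoint has two models within the same SAP. A programmer working from Appendix 15.2 would report a different estimate, SE and P value from one working from SAP 10.4. SAP Section 3 says that all final-analysis decisions will have been made before database lock. Here the text leaves one open.

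Second, the baseline score enters only by subtraction. Randomization keeps the change-score comparison unbiased. However, subtraction fixes the slope on baseline at 1, so it can over- or under-correct a chance baseline imbalance. In large samples it is never more precise than an ANCOVA with baseline as a covariate.

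**Working it through.** **Comparing the term lists**

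| Term | Protocol 10.3.2.4.1 | SAP 10.4 | SAP 15.2 |
|---|---|---|---|
| Treatment | yes | yes | yes |
| Region | yes | yes | yes |
| Index MI type | yes | yes | yes |
| Index MI management | yes | yes | yes |
| Type by management interaction | yes | yes | no |
| Age (continuous) | yes | yes | no |
| Diabetes | yes | yes | no |
| Peripheral artery disease | yes | yes | no |
| Prior MI | yes | yes | no |
| Baseline utility or VAS score | no | no | no |

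The protocol and SAP 10.4 lists are identical. Appendix 15.2 lacks five terms and adds none. The code in Appendix 15.5 does not settle the matter: it covers the Newcombe interval, Cox model, negative binomial model, covariate imputation and tipping point analysis, with no EQ-5D model.

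**Inputs for sizing**

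The plan states no SD, correlation, covariate R-squared or power for this endpoint, so there is no figure to reproduce. I take n = 8700 per group (Protocol 10.1.1) and assume complete EQ-5D data. The other inputs are assumptions shown over a range.

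**Size of the model conflict**

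Let R be the share of the variance of change, after treatment and strata, that the five extra terms explain. The unit is the SD of change after strata.

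- SE ratio, strata-only to nine-term: 1/sqrt(1 − R)
- SD of the difference between the two estimates: sqrt(2R/n)
- The same, in SEs of the nine-term model: sqrt(R/(1 − R))

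| R | SE ratio | SD of difference | In SEs |
|---|---|---|---|
| 0.01 | 1.005 | sqrt(0.02/8700) = 0.0015 | 0.10 |
| 0.05 | 1.026 | sqrt(0.10/8700) = 0.0034 | 0.23 |
| 0.10 | 1.054 | sqrt(0.20/8700) = 0.0048 | 0.33 |

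A simulation of 400 trials at R = 0.05 gave 0.0034 and 0.23, in agreement.

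**Size of the baseline omission**

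Let r be the correlation between baseline and Day 90, with equal SDs at both visits. The unit is now the SD of a single-visit score, so these figures are not on the scale of the previous table. The SD of change is sqrt(2(1 − r)) of this unit.

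- Variance, change score: 2(1 − r)
- Variance, ANCOVA: 1 − r²
- Precision lost: 1 − (1 − r²)/(2(1 − r)) = (1 − r)/2
- 95% half-width: 1.96 × sqrt(2 × variance/8700)

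| r | Variances (change, ANCOVA) | Precision lost | Half-widths (change, ANCOVA) | Difference |
|---|---|---|---|---|
| 0.2 | 1.60, 0.96 | 40% | 0.0376, 0.0291 | 0.0085 |
| 0.6 | 0.80, 0.64 | 20% | 0.0266, 0.0238 | 0.0028 |
| 0.8 | 0.40, 0.36 | 10% | 0.0188, 0.0178 | 0.0010 |

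With 7000 complete subjects per group the differences are 0.0094, 0.0031 and 0.0011.

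**Unequal SDs**

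With s0 and s1 the SDs at baseline and Day 90, the precision lost is (s0 − r·s1)² / (s0² + s1² − 2r·s0·s1). At r = 0.6:

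- s1/s0 = 1.5: (1 − 0.9)²/(1 + 2.25 − 1.8) = 0.01/1.45 = 0.7%
- s1/s0 = 0.75: (1 − 0.45)²/(1 + 0.5625 − 0.9) = 0.3025/0.6625 = 46%

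The loss depends strongly on this ratio, but the expression cannot be negative.

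**The case against.** The strongest reply is that only the first point is an error. All three passages agree in leaving baseline out, and a change-score ANOVA is a valid prespecified analysis. The absolute gain from adding baseline is at most about 0.009 SD. Adding it would also turn a model on which the protocol and SAP 10.4 agree into a declared departure. It is fair that the second point is an improvement and not a correction, and that the contradiction is cured by aligning the appendix alone.

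The sizing can also be challenged. Baseline is taken at screening, within days of the index MI, so equal SDs are not self-evident. Strictly, r should be a partial correlation given the covariates already in the nine-term model. Both remarks stand. The 40%, 20% and 10% figures illustrate the loss and do not bound it for this trial. The direction does not change.

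On precedence, one can argue that Section 5 declares no departure and so points to the protocol model, which is the SAP 10.4 model. That is a sensible inference, and Appendix 15.2 is probably the text that was not updated. It remains an inference. The appendix is headed as the analysis of the questionnaire, is cited from SAP 10.4 for detail, and is not labelled a sensitivity analysis.

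**Conclusion.** Both points hold. The contradiction rests on the text alone and needs no assumption. Its numerical effect is modest: over the assumed R of 1% to 10%, the two estimates would typically differ by a tenth to a third of an SE. The loss from omitting baseline can be sizeable in relative terms but is small in absolute terms at this sample size. It rests on an assumed correlation and SD ratio.

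No confirmatory conclusion is affected. SAP 10.4 classes the endpoint as exploratory and its P values as descriptive. This is a minor point, worth fixing because the fix is nearly free.

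**What to change.** State one model in both SAP 10.4 and Appendix 15.2: the nine SAP 10.4 terms plus the baseline utility score or baseline VAS score, as applicable. Delete the strata-only list from Appendix 15.2. Record the added covariate in SAP Section 5 as a change from the model in Protocol 10.3.2.4.1. If the team prefers not to add baseline, still replace the appendix list with the SAP 10.4 terms. Either change should be made before unblinding.

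The cost is one replaced term list, one covariate already collected and one declared departure. No subjects are lost: a change score already requires both values, and SAP 8.1.1 already imputes missing diabetes, peripheral artery disease and prior MI in a completed dataset intended for the planned analyses.

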10.5 Treatment Compliance

The compliance with the study treatment will be summarized at each infusion and overall.

A subject is considered to be compliant with the investigational product if at least 80% of investigational product is administered. The portion of investigational product administered is determined using the algorithm $\left(\frac{\text{actual volume infused}}{\text{planned volume}}\right) * 100\%$.

A binary variable (yes/no), associated with each infusion, will be defined to determine whether or not a subject is compliant. A subject will be considered to be compliant overall if each dose administered for that subject is compliant.

At each of the four infusions, number of subjects receiving the infusion, number compliant, and the portion of IP administered will be summarized. At infusions 2-4, the time interval between successive doses will be categorized as <5 days and ≥ 5 days; the number (%) of subjects in each interval will be presented. The number of days between successive doses will also be summarized as a continuous variable.

The following listing will be provided:

- Compliance with individual infusions and across all infusions overall

11 Safety Analyses

All analyses described in this section will be based on the Safety Analysis Set as defined in [Section 6.5](#).

11.1 Extent of Exposure

The extent of exposure to the study treatment will be summarized based on the Safety Analysis Set.

A cross tabulation of treatment randomized and treatment received will be generated. The treatment received category will also include randomized but not treated subjects.

Exposure to the investigational product will be descriptively summarized overall:

- Number of infusions (partial or complete) administered per subject
- Number of complete infusions administered per subject where a complete infusion is defined as receipt of at least 80% of planned infusion

Following data will be summarized for each infusion:

- Volume of infusion (mL) including any interruption(s)
- Duration of infusion (hours)
- Number of subjects with 0, 1, 2, or 3 or more infusion interruptions
- Cumulative duration of interruption (hours)
- Location of infusion administration including hospital, infusion center, or doctor's office or clinic

IP Overdose is defined as any single infusion with an infusion volume exceeding 150% the planned volume ($170*1.5 = 255$ mL) or an infusion rate that exceeds 3 mg of sucrose/body weight (kg)/duration of infusion (min) where infusion rate is calculated as [\(actual infused volume/170\)*9900/\(duration of infusion*weight\)](#). The 6g dose of CSL112 contains 9.9 g or 9900 mg of sucrose. The total number of subjects experiencing overdose will be presented by counting subjects once regardless of the number of overdoses that occur for a given subject.

The listing of individual subject data will include all variables presented in the summary table.

